2.0 HYPOTHESES AND STUDY OBJECTIVES

2.1 Hypotheses

Our primary objective is to compare two different implementation strategies to facilitate ongoing MOH efforts to scale up evidence-based depression treatment within NCD care. Specifically, we hypothesize that:

H1. Compared to providers at clinics receiving the basic implementation package, providers at clinics receiving the enhanced implementation package will deliver depression treatment with greater fidelity.

H2. Compared to patients receiving care at clinics with the basic implementation package, patients receiving care at clinics with the enhanced implementation package will be more likely to achieve depression remission at 6 and 12 months.

H3. Compared to patients receiving care at clinics with the basic implementation package, patients receiving care at clinics with the enhanced implementation package will be more likely to have well controlled hypertension and diabetes at 6 and 12 months.

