3.0 METHODOLOGY

We will conduct a clinic-randomized trial (RCT) to determine the best way to integrate evidence-based depression treatment into non-communicable disease (NCD) clinics in Malawi. We will compare implementation of depression treatment using (1) a basic implementation package vs. (2) an enhanced implementation package.

The basic implementation package will involve identifying an internal coordinator who is one of the full-time on-site providers at the clinic. The internal coordinator provides mentoring to peers and support to leadership in implementing the treatment program and aligning it with clinic priorities.

The enhanced implementation package will combine the internal coordinator with an external quality assurance committee. This committee will complete quarterly audits at the facility to evaluate compliance with the depression treatment protocol as well as providing

high-level support in implementing the treatment program through clinical expertise and limited on-site presence.

Clinics will be randomized 1:1 to receive either the basic or the enhanced implementation package. Clinics will then implement depression treatment as part of standard care at their NCD clinics. All patients at each clinic will receive that clinic's standard care.

To evaluate patient health outcomes, we will enroll a cohort of patients from each NCD clinic. (Sample size and inclusion criteria are below.) Participants will complete assessments at baseline and 6 and 12 months. Assessments will measure sociodemographics, depressive severity, self-reported health, and key medical, structural, and psychosocial factors including trauma history, intimate partner violence, other violence in the home, socioeconomic measures, coping, social support, self-efficacy, experiences of stigma related to mental health, medical and psychiatric comorbidity, and risk factors for hypertension and diabetes. Medical appointment attendance data will be abstracted from clinic records.

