3.2 Population

Patients at the participating NCD clinics who meet the following eligibility criteria will be invited to participate.

Inclusion criteria

1. Ages 18-65 years (antidepressant treatment considerations differ for those <18 or >65 years, and these age groups are expected to be very rare in the target clinics),
2. Current or new patient receiving care for either hypertension or diabetes from the NCD clinic at a study site listed in Section 3.1, and
3. Elevated depressive symptoms (PHQ-9 score ≥ 5).

Exclusion criteria

Patients will be excluded if they have a history of bipolar or psychotic disorder, or show emergent threat of self-harm.

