3.3 Duration

The Phase II RCT will occur during project years 2-4 (November 2018-October 2021). We will complete training for providers and staff in the two arms. We will initiate the two implementation strategies at all clinics and spend 24 months recruiting participants. Follow-up monitoring will extend an additional 12 months, through year 4.

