4.0 STATISTICAL ANALYSIS PLAN

Analysis of implementation and effectiveness outcomes will be intent-to-treat comparisons between arms. Comparisons will be made using generalized estimating equation models with a log link and binomial error distribution to compare proportions. The design effect introduced by clinic-level randomization will be addressed using the bias-corrected robust variance estimate for GEE models recommended given the small number of clusters. A secondary, as-treated analysis will restrict the analysis to those who received a minimum

dose of the depression treatment program (e.g., at least three depression care management appointments).

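### The secondary analysis restricted to patients who reached a minimum dose compares groups formed after randomisation, with no adjustment, time window or caution stated

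*Combined protocol and SAP*

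**What the plan says.** Section 4.0 plans intent-to-treat comparisons between arms, using a log-link binomial GEE with a small-sample variance correction. One further sentence follows: "A secondary, as-treated analysis will restrict the analysis to those who received a minimum" dose of the programme. The cut-off, "at least three depression care management appointments", is introduced as an example and not as a rule. No covariate, weighting, counting period or comment on interpretation is given, and no other section mentions this analysis.

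Three other places bear on it:

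- Section 2.1, H1, expects that "providers at clinics receiving the enhanced implementation package will deliver depression treatment with greater fidelity".
- Section 3.0 says the committee in the enhanced package will "complete quarterly audits at the facility to evaluate compliance with the depression treatment protocol".
- Section 2.1, H2, says enhanced-arm patients "will be more likely to achieve depression remission at 6 and 12 months", while Section 3.4 describes the primary outcome as a 3-month one.

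**The concern.** Attendance is observed after clinics are randomised. If the package changes which patients reach the dose, and those patients differ in prognosis, the two restricted groups are not comparable even though the arms were. That the package affects attendance is an inference from H1 and the audits; neither names patient attendance. It is a reasonable inference in a trial of strategies meant to improve delivery.

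Two errors are possible. With no true effect, the subset can show a difference in either direction. Conversely, if the package works by getting more patients treated, restricting to treated patients removes that effect from view.

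The missing time window is a separate fault. As written, an appointment after the 6-month visit could count towards dose for the 6-month outcome. The outcome times (3 months in one section, 6 and 12 in another) do not let the reader infer a window.

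The label is also unclear. Keeping the randomised arms and dropping patients below a dose is closer to a per-protocol analysis than to an as-treated one.

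**Working it through.** **Inputs from Section 3.4:** 40% remission with the basic package, 15-point target difference, two-sided 5% level, 80% power, ICC 0.02, 10 clinics, 116 per clinic, 90% retention. **Assumed, because the documents give no figures:** attendance by arm, and remission by attendance group.

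**1. The plan's own figure.** With unpooled variance, n per arm before clustering = (1.960 + 0.842)² × (0.40×0.60 + 0.55×0.45) / 0.15² = 170.06. Solving 5m / (1 + 0.02(m − 1)) = 170.06 gives m = 104.2 per clinic, and 104.2 / 0.90 = 115.8, rounded up to 116. The sample size reproduces. It covers the intent-to-treat comparison only.

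**2. Bias with no true effect.** Let share A reach the dose in either arm (remission rA), share C reach it only under the enhanced package (rC), and the rest never reach it; overall remission is 40% in both arms. The restricted rates are rA (basic) and (A·rA + C·rC)/(A + C) (enhanced), so

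bias = C/(A + C) × (rC − rA).

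| A, C | Attendance gap | rA 45%, rC 37.5% | rA 50%, rC 35% |
|---|---|---|---|
| 0.40, 0.05 | 5 points | −0.8 | −1.7 |
| 0.40, 0.10 | 10 points | −1.5 | −3.0 |
| 0.40, 0.20 | 20 points | −2.5 | −5.0 |
| 0.30, 0.30 | 30 points | −3.75 | −7.5 |
| 0.30, 0.40 | 40 points | −4.3 | −8.6 |

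Swapping rA and rC reverses each sign. Risk ratios run from 0.94 to 1.09 for gaps of 5 to 10 points, and from 0.83 to 1.25 for gaps of 20 to 40.

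**3. When the bias is zero.** Take two equal prognosis groups with 55% and 25% remission, and write attendance as good/poor prognosis.

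- Dose unrelated to prognosis: 40/40 in basic, 60/60 in enhanced, gives 40.0% vs 40.0%.
- Package does not change who attends: 60/20 in both arms gives (60×0.55 + 20×0.25)/80 = 47.5% in each.
- Attendance raised by the same ratio in both groups: 60/20 to 90/30 gives (90×0.55 + 30×0.25)/120 = 47.5%, again equal.

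The documents do not show that any of these holds.

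**4. Equal attendance is not proof of no bias.** Suppose 30% are dosed in either arm (45% remit), 10% only under basic (35%), 10% only under enhanced (50%), and 50% never (36%). Overall remission is 13.5 + 3.5 + 5.0 + 18.0 = 40% in both arms, and 40% are dosed in each. The restricted rates are 17.0/40 = 42.5% and 18.5/40 = 46.25%, a difference of +3.75 points.

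**5. False-positive rate.** Simulation with 5 clinics per arm, 104 followed per clinic (116 × 0.90 = 104.4), binomial numbers dosed, beta-binomial outcomes with ICC 0.02, log-link GEE with independence working correlation, and at least 100,000 trials per case. Section 4.0 names neither the variance correction nor the reference distribution, so two corrections with t on 8 df are shown.

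| Case | Mancl-DeRouen | Kauermann-Carroll |
|---|---|---|
| Zero bias | 3.1–3.2% | 4.8–4.9% |
| Gap 5, 45/37.5 | 3.2% | 5.0% |
| Gap 10, 50/35 | 4.6% | 6.9% |
| Gap 20, 45/37.5 | 4.3% | 6.4% |
| Gap 20, 50/35 | 7.7% | 10.9% |
| Gap 30, 50/35 | 12.8% | 17.5% |
| Gap 40, 45/37.5 (both signs) | 5.9–6.5% | 8.6–9.4% |
| Gap 40, 50/35 | 16.5% | 22.1% |
| Equal attendance, step 4 | 5.2% | 7.7% |

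Fitting an exchangeable GEE instead (1,500 trials each, Mancl-DeRouen, t 8 df) gave 3.1%, 4.8% and 16.0% for zero bias, gap 10 and gap 40 (both 50/35).

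**6. A hidden effect.** Let 1/3 be dosed under basic and 7/12 under enhanced, with remission 80% if dosed and 20% if not. Overall: 0.8/3 + 0.2×2/3 = 40.0% and 0.8×7/12 + 0.2×5/12 = 55.0%, the plan's target difference. In the subset: 80% vs 80%, risk ratio 1.00.

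**7. Cross-check with another model.** Let a 50/50 prognostic factor shift the log-odds of reaching the dose by ±1 and change remission by 20 to 40 points. The false difference is then 2.6 to 5.1 points at 30% vs 60% attendance, and 4.1 to 8.3 points at 20% vs 70%.

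**The case against.** The plan already bounds the hazard: intent-to-treat comes first, the restricted analysis is called secondary, and nothing says it will support or override the main result. That stands, and it limits the seriousness of the point. But calling an analysis secondary ranks it; it does not tell the reader that the comparison is non-randomised.

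The sizes rest on attendance and prognosis figures the documents do not contain. This also stands. With attendance gaps of 5 to 10 points the rejection rate stays close to its zero-bias level, and the 17% / 22% figures need both a 40-point gap and the larger prognosis difference. The 80% versus 20% example is deliberately extreme: it shows that the subset answers a different question, not that such an effect is likely.

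The protocol dates prove nothing about when the cut-off was conceived. Section 3.3 gives a scheduled end, and the change history does not say when this sentence entered the plan. That is why the fix asks only for the timing to be stated.

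Finally, counting only appointments before the outcome visit does not deal with patients who remit early and need fewer appointments. That is correct, and is one more reason to keep the result exploratory.

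**Conclusion.** The point holds as a cheap improvement to a secondary analysis. The textual part is certain: the subset is defined after randomisation, the cut-off is an example, and no window, adjustment or caution is stated. In general such a comparison is biased. Its direction and size here cannot be known from the documents. The illustrated range, on assumed attendance and prognosis, runs from zero to 8.6 points either way, against a target of 15. The intent-to-treat analysis and the 1,160 sample size are not affected.

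**What to change.** In Section 4.0:

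1. Keep intent-to-treat as the only basis for inference on the effect. State that the restricted comparison is non-randomised and exploratory, and is not evidence for or against the intent-to-treat result.
2. State one cut-off before outcomes are analysed by arm, or report several, and in either case say when they were chosen. Section 3.3 says "The Phase II RCT will occur during project years 2-4 (November 2018-October 2021", and the current protocol version is dated November 2022, so a cut-off set now cannot be assumed to be pre-specified.
3. Count only appointments before the outcome visit being analysed.
4. Adjust for baseline depressive severity, already collected (Section 3.0: "Assessments will measure sociodemographics, depressive severity, self-reported health"), noting that this may reduce the bias but need not remove it.
5. Report the proportion reaching the dose by arm, among all enrolled, as an additional treatment-delivery outcome under intent-to-treat with the same GEE. Do not present it as the H1 fidelity measure. Section 3.2 enrols from a PHQ-9 of 5 upwards, and the documents do not say that every such patient is expected to have three appointments.

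The cost is a few sentences, a little more analysis and no new data, since treatment delivery is already abstracted from clinical records (Section 3.5). The restricted result could no longer be offered as confirmatory, a use the plan does not claim for it.

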5.0 ETHICAL CONCERNS

5.1 Human Subjects

5.1.1 Institutional Review Board

Prior to implementation of this RCT, all protocol materials will be approved, as appropriate, by local institutional review boards (IRB) / ethics committees (EC) responsible for oversight of the evaluation including the National Health Sciences Research Committee of Malawi (NHSRC) and the Biomedical Institutional Review Board of the University of North Carolina at Chapel Hill. All research will adhere to Malawian and US ethical standards for research in human subjects.

5.1.2 Confidentiality, Risks, and Risk Minimization

Breach of confidentiality: There is always the possibility of a breach of confidentiality when conducting research. Disclosure of medical or other personal information about participants, particularly mental health status may result in negative stigma being associated with the individual and/or family. Our research team is very aware of the need for absolute confidentiality and has extensive experience in dealing with highly sensitive personal medical and family information. While we acknowledge that a breach of confidentiality is possible, we anticipate that the likelihood is very low because of the precautions that will be taken to protect confidentiality. Research data will be coded (with identifiers removed). The linking file that connects the codes to individual identities will be securely stored by the study team. Research data will be stored securely on password-protected machines or servers or in locked cabinets, with access restricted to study staff.

Mental health counseling sessions may be recorded so that supervisors can provide feedback to the counselors about the quality of their counseling. These recordings will be identified with a code number only and will not be shared with anyone outside the research team. If participants do not want their counseling sessions recorded, they can choose not to participate in the study. This information is included in the informed consent form.

Qualitative and cognitive interviews will also be recorded. These recordings will be identified with a code number only and will not be shared with anyone outside the research team. If participants do not want to be recorded, they can choose not to participate in the qualitative component of the study. This information is included in the informed consent form.

Psychological distress from interview questions pertaining to mental health: To expose participants to as little psychological distress as possible and to ensure protection of participant identities and confidentiality, all questions will be asked in a private place at the health facility or a private place of the participant's choosing. Interviews will be conducted by trained interviewers in a language in which the participant is comfortable responding.

Discomfort: Patients may experience discomfort from the collection of a small amount of blood for blood glucose monitoring. This risk will be minimized by using trained clinical staff for blood collection.

Indication of threat of harm to self or others reported in response to interview questions: Patients indicating such threat of harm during interviews will be referred to existing clinical

response pathways as defined by each clinic. For participants with indication of acute risk of self harm, research staff will ensure handoff to a clinical team member.

Protection from COVID-19: As of March 2020 the likelihood of Malawi experiencing initial cases and rapid escalation of COVID-19 is high, therefore we are adding the option of phone interviews in case there is a need to minimize exposure to the novel coronavirus to participants and staff.

5.1.3 Benefits to Participants

Participants will not receive any direct benefit from participating in the study. Whether or not they participate in the research component, all patients at the participating sites will receive that site's standard care.

The study will raise awareness about the diagnosis of depression, a condition that has received little research attention in sub-Saharan Africa. The study will also provide essential information about the potential reciprocal relationships between depression and NCD infection. This information will inform an appropriate intervention for depression in the future.

While this study has some risks associated with participation, we anticipate that few participants will experience negative events as a result of taking part in the study. The risk to individual participants is small and the potential benefit to society is substantial. Therefore, the risk/benefit ratio is favorable.

5.1.4 Costs and Compensation

Patients, providers, directors, and MOH officials invited to participate will receive a travel reimbursement equivalent to 10 USD for each research interview in which they participate. Participants will not assume any extra costs as part of this study.

5.1.5 Informed Consent

This protocol and the informed consent documents and any subsequent modifications will be reviewed and approved by the IRB and ethics committees responsible for oversight of the study: the Biomedical Institutional Review Board of the University of North Carolina at Chapel Hill and the National Health Sciences Research Committee of Malawi (NHSRC). All procedures conform to US and Malawian ethical standards regarding research involving human subjects.

Written informed consent will be obtained. Informed consent will clearly explain the purpose of the research, what will be required of the individual, and the risks and benefits of participation. For providers and clinic directors, the informed consent process will emphasize that the provider is free to participate or not; a decision not to participate will have no negative impact on his or her employment, evaluation, or anything else related to the workplace; and the provider is free to end participation at any time. For patients, the informed consent process will emphasize that the patient is free to participate or not; a decision not to participate will have no negative impact on any aspect of his or her clinical care; and the patient is free to end participation at any time. The informed consent process and all documents will be in the provider's or patient's preferred language (likely English for providers and Chichewa or Chitumbuka for patients). Participants will be presented an informed consent form with the above information and contact information for the PI, study personnel, and IRB. Illiterate participants will be asked to put their mark (in lieu of a signature) as a written sign of consent.

The investigators have experience obtaining informed consent for trials in Malawi and thus the informed consent process has been designed to maximize understanding of potential risks.

5.2 Adverse Event Reporting

We do not anticipate any adverse events occurring given the nature of the minimal risks associated with this research. However, in the case that a breach of confidentiality does occur, the study team will immediately inform the IRBs.

- Deaths related to study participation shall be reported by the PI to the NIMH and IRBs immediately and no later than within 5 business days of the PI first learning of the death
- Unexpected Serious Adverse Events related to study participation shall be reported by the PI to the NIMH and IRBs within 10 business days of the study team becoming aware of the SAE
- Unanticipated Problems Involving Risks to Subjects or Others shall be reported by the PI to the NIMH and IRBs within 10 business days of the study team becoming aware of the problem
- Adverse events and SAEs, including deaths, that are deemed expected and/or unrelated to the study shall be submitted in summary form to the NIMH and IRBs with the annual progress report
- Protocol violations shall be submitted in summary form to the NIMH and IRBs with the annual progress report

5.3 Study Discontinuation

The study may be discontinued at any time by the UNC IRB, the NHSRC, the Office for Human Research Protections (OHRP), or other government agencies as part of their duties to ensure that research participants are protected.

6.0 PUBLICATION AND DISSEMINATION OF RESEARCH FINDINGS

Local dissemination of evaluation results is critical to the success of this project. We will conduct a data interpretation workshop during which we will work with stakeholders to present preliminary findings. This workshop will serve as a platform for discussion of involved staff, stakeholders, and ministry officials through which we will frame the implications of the evaluation results. Subsequent dissemination meetings after the data are fully analyzed will emphasize development of a data use plan from which stakeholders, staff, and ministry officials will help to guide the local dissemination agenda and target audiences. Given the scope of this proposal and its intended audience, we have identified some venues that are likely to be a suitable target for dissemination. A venue of particular interest is the Annual Malawi Mental Health Research and Practice Conference sponsored by the Department of Mental Health at the College of Medicine. Where possible we will also submit abstracts to regional and international venues. Publication of the findings is expected in peer reviewed scientific journals. The results of this evaluation will be published and will be integral to understanding the role of depression treatment in NCD clinics in Malawi. However, any presentation, abstract, or manuscript will be made available for review to the NCDs and Mental Health unit at the Ministry of Health and the NHSRC.

In addition to presentation at local and regional conferences, all involved clinics will receive a formal presentation regarding program outcomes and proposed next steps. In coordination with our stakeholders and partners in the Ministry of Health, we will also develop presentations that are geared specifically to local clinics that were not involved in the program, transferring relevant information and “lessons learned” from on-the-ground healthcare workers. Our goal of result dissemination is directly relevant to our capacity building objectives with stakeholders – stakeholders, including clinical staff involved in the implementation of the proposed intervention, will be actively involved in the framing and contextualization of results prior to presentation or publication.

